6.1.13 Diaries

Subjects or subjects' parent or guardian will be required to complete the following:

- Intake Diaries, completed daily, which will include:
 - PN/IV volume and calories (days per week, hours per day)
 - EN (formula and specialized electrolyte solutions) volume and calories (days per week, hours per day)
 - Other Nutrition (regular diet and drink) intake (to be converted into calories by site personnel)
- Urine/Stool Output Diary, completed for 2 days (48 hours) just prior to every scheduled clinic visit and telephone contact, consisting of :
 - Collection of urine data:
 - For those who are toilet trained and NOT IN DIAPERS: All urine output should be measured and recorded in mL. The subject or parent will perform dipstick specific gravity tests on the first urine produced after the daily infusions of PN/IV support.
 - For those who are not toilet trained and IN DIAPERS: The weight of all urine-only diapers will be recorded. Volume will be calculated based on the formula: 1g (scale weight) = 1 mL or 1 cc. At the discretion of the investigator, the parent may be asked to collect the first void after the daily infusion of PN/IV support to measure the specific gravity.
 - Collection of stool output data (including stool only and mixed urine/stool diapers):
 - For those who are toilet trained and NOT IN DIAPERS: Daily stool count will be recorded.
 - For those who are not toilet trained and IN DIAPERS: The weight of all diapers that contain stool (including diapers that contain mixed stool and urine) will be recorded as stool output. Stool volume will be calculated based on the formula: 1 g (scale weight = 1 mL or 1 cc).
 - All ostomy output will be recorded as stool output and measured in cc or mL.
 - In addition all subjects (toilet trained or not) will report on the average consistency (form) of the stool passed each day during the 48-hour

period. The subject or parent will use the Bristol Stool Form Scale (Lewis and Heaton, 1997) to make the assessment.

During the screening period, these diaries focusing on Intake and Output will be completed every day.

All diaries will be reviewed by the investigator or their designee at each visit or telephone contact to assess clinical status and opportunity for PN/IV changes and advance in feeds. At each visit, the diaries will be reviewed for completeness and accuracy of the data.

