APPENDIX 1: CONSIDERATIONS FOR MANAGEMENT OF NUTRITIONAL SUPPORT DURING THE STUDY

Please consider the following clinical parameters identified as markers for adequate management of pediatric short bowel syndrome. These parameters should also be considered for managing nutritional support (PN/IV and/or oral/enteral feeding) in terms of volume and calories during the treatment period.

- Considerations to adjust nutritional support in volume and calories will be made at all planned visits.
- Maintaining growth (including weight and length and head circumference [for children up to 36 months of age]) by the subjects trending along their growth chart and adjusting calories/volumes to maintain appropriate growth.
- Other clinical evaluations
 - Normal serum electrolytes
 - Stable BUN/creatinine levels
 - Decrease in stool frequency or volume, including mixed output
 - Stool consistency (ie, Bristol Stool Scale)
 - Urine specific gravity
- General consideration to possible clinical deterioration in SBS
 - Inability to maintain weight and growth velocity
 - Diarrhea (≥ 10 bowel movements per day, ≥ 80 mL/kg/day from an ostomy, or ≥ 75 mL/kg/day mixed output)
 - Colic/vomiting frequency increased
 - Electrolyte changes or imbalance
 - Skin breakdown
- Adjustments should be based on the actual nutritional support in volume and calories the subject infuses. Subjects should remain compliant with the nutritional support prescription in volume and calories during the study.
- Nutritional support constituents may be adjusted at the discretion of the investigator.
- During the 48-hour Intake/Output measurement period prior to the subject's scheduled visit, no further changes to the prescribed nutritional support should be made.
- If there is a change in EN or other oral fluid intake, the investigator should consider this when adjusting the PN/EN support in volume and calories.

Figure A-1 Weaning Algorithm for Subjects Who are NOT Toilet Trained and in Diapers

[figure not shown]

Figure A-2 Weaning Algorithm for Subjects Who are Toilet Trained and NOT in Diapers

[figure not shown]
[figure not shown]

Figure A-3 Clinical Dehydration Assessment and PN/EN Adjustment

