7.5. STATISTICAL TESTS

Due to the limited size of the study population descriptive statistics will be used with a goal of summarizing the sample. As such, no claims of significance will be made for any of the data.

Continuous variables, including those assessed on a discrete scale, will be summarized using descriptive statistics including number of subjects, mean, median, standard deviation, maximum, and minimum. For categorical variables, statistical summaries will include number of subjects and percentages.

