7.6. COMMON CALCULATIONS

For quantitative measurements, change from baseline will be calculated as:

Test Value at Visit X – Baseline Value

Percent change from baseline will be calculated as:

$$\frac{((\text{Test Value at Visit X} - \text{Baseline Value}) / \text{Baseline Value}) * 100}{}$$

Change (or percent change) from baseline tables will be calculated based on the number of subjects in the treatment group with a non-missing value at baseline and at the time point being analyzed.

Document:	\\quintiles.net\Enterprise\Apps\sasdata\SASa\sas\Shire\Teduglutide\Biostatistics\Documentation\SAP\TE D-C14-006_SAP_Final_V1.0_20170714		
Author:	PPD	Version Number:	Final V1.0
		Version Date:	14Jul2017
Template No:	CS_TP_BS016 – Revision 3	Reference:	CS_WI_BS005
Effective Date:	01May2012		

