12.2. GASTROINTESTINAL SYMPTOMS HISTORY

The following Gastrointestinal Symptoms History collected at Baseline will be summarized based on categories of not present, mild, moderate, and severe, with clinical significance also summarized where the event is present:

- Abdominal/belly pain
- Nausea/feeling queasy
- Vomiting/throw up
- Heartburn/reflux/spit up
- Gas/bloating
- Diarrhea/loose stool
- Constipation/very hard stool

A listing will also be presented by treatment group and subject identifier.

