19.8. FECAL AND URINE OUTPUT

Urine and stool output data is recorded over a 48 hour period of PN/IV and EN stability before every scheduled site visit and within 1 week of implementing any PN/IV prescription adjustment.

The average daily urine output (mL/kg/day) at the scheduled site visit will be calculated as follows:

$(\text{Total urine output over 48 hours} / 2) / \text{body weight (kg) at the scheduled visit}$

where total urine output is calculated as the sum of the urine output in mL and the urine-only diaper weights in g (1g = 1mL) for the subject collected on the output diary form of eCRF. Values will not be calculated if the urine output is not available at the visit. If the body weight at the scheduled visit is missing, the last available weight assessment will be used.

The average daily fecal output will be summarized separately by the average number of stools per day, the average typical stool form score using Bristol Stool Form Scale, the average total daily stool/mixed stool diaper weight (g/kg/day) and the average ostomy output per day (mL/kg/day) for each visit. The average number of stools per day and the average typical stool form score will be calculated as (sum of the daily data in a 48-hour period / 2). The body weight will be used to calculate the daily stool/mixed stool diaper weight (g/kg/day) and the total ostomy output per day (mL/kg/day) using the same formula as we use for calculate the average daily urine output.

The change and the percent change in average daily output for stool and urine from baseline to each scheduled visit, as well as at EOT, will be presented by treatment group using descriptive statistics. The change and the percent change in average daily output for fecal and urine output from baseline to each scheduled visit, as well as at EOT, will be presented by treatment group using descriptive statistics. A listing will also be provided.

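### Percent change in the Bristol stool form score (SAP 19.8) is not interpretable, and the sign of its mean change does not show better or worse; category counts and a shift table would show it

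*SAP*

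**What the plan says.** SAP 19.8 divides average daily fecal output into four separately summarised measures: stool count, stool form, diaper weight per kg and ostomy output per kg. The second is "the average typical stool form score using Bristol Stool Form Scale". It is derived per subject as a two-day mean: "the average typical stool form score will be calculated as (sum of the daily data in a 48-hour period / 2"). The section then presents "The change and the percent change in average daily output for fecal and urine output from baseline to each scheduled visit", and at EOT, by treatment group with descriptive statistics, and adds a listing. It plans no category counts and no shift table for stool form.

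Two general rules feed into this. SAP 7.5 states: "Continuous variables, including those assessed on a discrete scale, will be summarized using descriptive statistics", namely n, mean, median, SD, maximum and minimum. SAP 7.6 defines percent change as the change divided by the baseline value, times 100.

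On the meaning of the score, Protocol 6.1.13 says that the subject or parent "will report on the average consistency (form) of the stool passed each day during the 48-hour" collection period, using the Bristol scale. SAP 12.2 lists loose stool as a GI symptom and also lists "Constipation/very hard stool". Protocol Appendix 1 names "Stool consistency (ie, Bristol Stool Scale") among the clinical evaluations without giving a direction. For stool frequency and volume, by contrast, it names a decrease.

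**The concern.** Stool count, diaper weight and ostomy volume are quantities with a true zero, and change and percent change suit them. A form score is a category label. Dividing by its baseline value gives a percentage that depends on which end of the scale is numbered 1. The signed change has a different problem. The plan treats both ends of stool form as symptoms, so a fall can be a move from loose toward the middle or from the middle toward hard.

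At stake is the readability of one descriptive safety table. Protocol 4.1 plans at least 10 subjects per dose arm, so a few children determine each mean. The score appears beside three measures for which a fall is easily taken as good news, which invites the same reading here.

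**Working it through.** **No figure to reproduce.** The plan states no expected value for this variable. The check applies the SAP's own formulas to illustrative groups.

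**Inputs from the documents.** Change = visit - baseline, and percent change = 100 x (visit - baseline) / baseline (SAP 7.6). Summaries are those of SAP 7.5. The group size of 10 follows Protocol 4.1.

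**Assumptions, not in the documents.** Scores run from 1 (hardest) to 7 (loosest), and 3 to 5 is taken as the middle range. The baseline mix of loose and hard stool is not given, so several mixes are shown.

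**Step 1: the sign and size of a single change.**
- 7 to 4 (loose to middle): change -3; 100 x (-3)/7 = -42.9%.
- 4 to 1 (middle to hard): change -3; 100 x (-3)/4 = -75.0%.

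The absolute changes are identical, and the move to hard stool has the larger percent fall.

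**Step 2: dependence on numbering.** 6 to 4 gives 100 x (-2)/6 = -33.3%. With the scale numbered in reverse, the same step is 2 to 4, which gives 100 x 2/2 = +100%.

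**Step 3: groups of 10.**

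| Case | Mean change | Median change | SD | Min, max | Mean % change | In 3-5, baseline to visit |
|---|---|---|---|---|---|---|
| A: all 6 to 4 | -2 | -2 | 0 | -2, -2 | -33.3 | 0 to 10 |
| B: all 6 to 1 | -5 | -5 | 0 | -5, -5 | -83.3 | 0 to 0 |
| C: five 6 to 4, five 2 to 4 | 0 | 0 | 2.11 | -2, +2 | +33.3 | 0 to 10 |
| D: five stay at 6, five at 2 | 0 | 0 | 0 | 0, 0 | 0.0 | 0 to 0 |
| E: five 4 to 6, five 4 to 2 | 0 | 0 | 2.11 | -2, +2 | 0.0 | 10 to 0 |
| F: eight 6 to 4, two 2 to 4 | -1.2 | -2 | 1.69 | -2, +2 | -6.7 | 0 to 10 |
| G: nine 6 to 4, one 2 to 4 | -1.6 | -2 | 1.26 | -2, +2 | -20.0 | 0 to 10 |

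In C every child reaches the middle, and in E every child leaves it. Their absolute-change summaries are the same in all columns. B shows a larger fall than A although nobody in B ends in the middle range. F and G show that the offset in absolute change is only partial when the mix is uneven. Percent changes do not cancel in C; they give a net rise although every child reached the middle.

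**Step 4: influence of one child among ten.**
- Nine 7 to 4 plus one 4 to 1: mean change = (9 x (-3) - 3)/10 = -3.0; mean percent change = (9 x (-42.86) - 75)/10 = -46.1%, against -42.9% without that child.
- Nine 7 to 4 plus one 1 to 4 (+300%): mean percent change = (9 x (-42.86) + 300)/10 = -8.6%; the median percent change stays at -42.9%.

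One child moving to hard stool barely moves the means and so does not stand out. One child starting at the hard end swings the mean percent change.

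**The case against.** The strongest reply is that nothing is lost. SAP 19.8 summarises the score at each visit, and the default statistics include median, SD, minimum and maximum. A child at the hard end would appear as the visit minimum. The visit values would also separate cases C and E: in C the range narrows from 2-6 at baseline to 4-4 at the visit, and in E it widens from 4-4 to 2-6. A listing is provided, and GI symptoms are collected as adverse events. The variable is minor: Protocol 8.2 and 8.3 define fecal output by volume or number of bowel movements, without stool form, and SAP 7.5 makes no significance claims. The population may also be mostly at the loose end at baseline, which would limit offsetting. All of this stands, and it keeps the point small.

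Two stronger readings are tempting. A reader might infer that the plan counts hardening stool as further improvement. It does not: no section gives the score a direction of benefit, a responder rule or an improvement label. A reader might also connect hard stool with intestinal obstruction, which Protocol 6.1.4 lists as an identified risk. Neither document links stool form to it.

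It can also be said that the phrase about daily output was not meant to cover a form score. The table shells are in a separate file, so this cannot be excluded. But 19.8 itself makes the score one of the measures of fecal output, so its inclusion is the natural reading.

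What the reply does not answer is that the planned percent change has no usable meaning, and that no planned summary counts children in the hard, middle and loose ranges.

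**Conclusion.** The point holds as a low-priority improvement. Percent change of the form score is not interpretable under any numbering. Mean change is computable, but its sign does not separate movement toward the middle from movement away. That both ends matter rests on the documents (SAP 12.2). The sizes shown rest on the assumed 1-to-7 coding and 3-to-5 middle range. Full offsetting needs a balanced baseline mix and occurs only in absolute change; at 8:2 and 9:1 the mean change is -1.2 and -1.6 against -2 with no offsetting. The consequence is a supplementary safety table that can be misread. The data are kept, and the primary endpoint is not affected.

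**What to change.** In SAP 19.8:
- Drop percent change for the stool form score, and do not rely on its mean change.
- Add n and % by dose group and standard of care at each scheduled visit and EOT, plus a baseline-to-visit shift table, in three exhaustive categories of the 48-hour average. One option is below 3 (hard), 3 to 5 (middle) and above 5 (loose), with the cut-offs declared as an assumption. Two-day means can be 2.5 or 5.5, so whole-number bands such as 1-2, 3-5 and 6-7 would leave values unassigned.
- State what happens when only one of the two days is recorded. Section 19.8 gives no rule, and the fixed divisor would turn a single recorded 6 into 6/2 = 3.0, which falls in the middle category.
- Keep change and percent change for stool count, diaper weight and ostomy volume.

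The SAP already uses this kind of display: shift tables for laboratory values (19.2) and category incidence for ECG (19.7). The cost is SAP wording and one table shell, with no new data. The downside is that moves within a category, such as 7 to 6, would appear only in the listing.

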8.3 Pharmacodynamic Variables

The following pharmacodynamic parameters will be measured:

- PN/IV volume reduction of at least 20% at 24 weeks (or EOT) compared to baseline

- 100% reduction in PN/IV support (any subjects who are able to completely wean off PN/IV support) compared to baseline at EOT
- Change from baseline (absolute and percent change) in PN/IV support (volume and calories), citrulline, and enteral nutritional support (volume and calories) over time
- Change from Week 24 (or EOT) (absolute and percent change) in PN/IV support (volume and calories), citrulline, and enteral nutritional support (volume and calories) at Week 28 (or EOS)
- Change in body weight, height (or length) and head circumference (up to 36 months of age). Derived variables will include height Z-score, weight Z-score, body mass index (BMI), and BMI Z-score
- Fecal output (by volume or number of bowel movements per day)
- Change in hours per day and days per week of PN/IV support
- Proportion of responders (ie, subjects who achieve at least a 20% reduction in PN/IV volume) over time

Descriptive statistics (mean, median, standard deviation, minimum and maximum values, the number and percentage of subjects in specified categories) will be calculated to summarize the absolute values and change from baseline at each scheduled visit for each treatment group.

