8.3. MISSING DATA

Missing data will in general not be imputed. However, partial dates will contribute to analyses as described in [Appendix 2](#). All available data will be included in the safety analysis.

Details for the imputation algorithm for the missing endpoint values for PN/IV support parameters (volume, calories and etc.) will be described in Section [17.1.1](#) of this analysis plan.

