Days per week of actual PN/IV support for all visits except the baseline visit will be calculated as follows:

Days per week of actual PN/IV support = (number of days with non-zero values for PN/IV volume within the 7 days prior to the visit / number of days for which any PN/IV intake data is recorded within the 7 days prior to the visit) * 7

For the week 1 visit, data prior to the baseline visit will not be used for the calculation.

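### SAP 19.8 divides the 48-hour stool form score by a fixed 2, which suits a count but not a rating that can be absent on one of the two days (minor)

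*SAP*

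**What the plan says.** SAP 19.8 lists four fecal output summaries, one of which is "the average typical stool form score using Bristol Stool Form Scale". The number of stools and the form score share a derivation: "the average typical stool form score will be calculated as (sum of the daily data in a 48-hour period / 2". The section then plans "The change and the percent change in average daily output for fecal and urine output from baseline to each scheduled visit", and at EOT, by treatment group with descriptive statistics. Its only sentence about unavailable data concerns urine output. It says nothing about a day without a form score.

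Protocol 6.1.13 describes what is rated: every subject, toilet trained or not, "will report on the average consistency (form) of the stool passed each day during the 48-hour" period. For toilet-trained children the same section says "Daily stool count will be recorded", so among them a stool-free day can be recognised as a count of zero.

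Three other SAP sections bear on the denominator:

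- SAP 8.3 says "Missing data will in general not be imputed", without saying how to average an incomplete window.
- SAP 17.1.1 divides PN/IV diary sums by the number of days that have a value, and extends that approach to the remaining averaged diary measures.
- SAP 17.2.1.7 takes the same line for days per week of PN/IV support, where the divisor is the "number of days for which any PN/IV intake data is recorded within the 7 days prior to the visit".

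**The concern.** A stool count adds up over days. A day with no stool contributes zero, and dividing the two-day total by 2 gives the correct daily average. A form score does not behave in that way. It describes stool that was passed, and a day without stool gives nothing to describe. Dividing by 2 regardless treats the absence of a score as though it were a score of zero. An unfilled diary day raises the same problem.

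What is at stake is a misleading line in a descriptive table. A child whose stool form never changed could be shown with a large fall at one visit, or could drop out of that visit's summary, depending on how the programmer reads a formula that does not cover the case.

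**Working it through.** The plan gives no numerical result for this derivation, so there is no figure to reproduce. The check is direct arithmetic.

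**Inputs.** The formula is from SAP 19.8. The arm size of 10 is the minimum per treatment arm in Protocol 4.1. The score of 6 is chosen for illustration; the halving does not depend on it.

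**Step 1: both days scored.** The fixed-divisor rule and the mean over scored days agree. Scores of 6 and 6 give (6 + 6)/2 = 6.0; scores of 5 and 7 give (5 + 7)/2 = 6.0.

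**Step 2: one day unscored.** There are three ways to process a window with a single score s:

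- Skip the unscored day or count it as 0, and keep the divisor at 2: s/2. With s = 6 this is 3.0, and against a baseline of 6 the change is (3 - 6)/6 = -50%.
- Set the window to missing: no value, and the child leaves that visit's summary.
- Divide by the number of scored days: s/1 = 6.0, a change of 0%.

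**Step 3: one arm.** Take 10 children, all truly at 6 at baseline and at the visit, with k of them having one unscored day in the visit window. Under the first reading, the arm mean is (6(10 - k) + 3k)/10 and the mean percent change is -50k/10.

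| k | Mean, divisor kept at 2 | Mean percent change | n if set to missing | Mean over scored days (n = 10) |
|---|---|---|---|---|
| 1 | 5.7 | -5% | 9 | 6.0 |
| 2 | 5.4 | -10% | 8 | 6.0 |
| 3 | 5.1 | -15% | 7 | 6.0 |

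If the windows are set to missing, the mean of the remaining children is still 6.0, because all children are alike in this illustration. The shift from one affected child shrinks as the group grows: in a pooled group of 20 with k = 1, the mean is (6 × 19 + 3)/20 = 5.85 and the mean change is -50/20 = -2.5%.

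**Step 4: how often.** Neither document gives a frequency. If each day were unscored with probability p, independently, the chance that exactly one of two days is unscored is 2p(1 - p). For p of 1%, 5%, 10% and 20% this is 2.0%, 9.5%, 18.0% and 32.0%. These values of p are assumptions that only show the range.

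**Step 5: does SAP 17.1.1 already settle it?** Its denominator is the suitable one, and its reference to other averaged diary measures could be read to include stool form. Three things stand against that. The measures it names are all nutritional. Its limits on missing days (more than 2 in a week, more than 5 in two weeks) are built for 7- and 14-day windows; a two-day window can never have more than 2 days missing, so the limit could never apply. And 19.8 states its own divisor for this variable. The two sections therefore point to different denominators, and neither says which governs.

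**The case against.** The strongest reply is that the premise is inferred. Neither document says what is entered for form on a stool-free day, and diary or eCRF instructions may deal with it. The SAP is written to Protocol Amendment 4, whereas the history in the protocol at hand ends at Amendment 2. Strictly, a sum with an undefined term has no value, so 19.8 is silent rather than plainly wrong; halving needs a further programming choice. Setting an incomplete window to missing is a defensible completeness rule under SAP 8.3. A programmer could also cite SAP 17.1.1 for the denominator recommended here. All of this stands. It limits the point to an unhandled case in a stated formula; it does not make a fixed divisor suitable for a rating.

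Some stronger readings are tempting but not supported:

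- A reader might infer that the baseline value would be distorted in the same way. SAP 19.8 does not define a 48-hour baseline window, output diaries are kept daily during screening (Protocol 6.1.13), and SAP 7.2 takes the last non-missing measurement as baseline.
- A reader might take constipation on the symptom list in SAP 12.2 as evidence that stool-free days are common. A checklist item says nothing about frequency.
- Because Protocol Appendix 1 names stool consistency among the considerations for nutritional support, a reader might infer an effect on weaning and hence on the primary endpoint. Investigators review the diaries themselves at each contact; the SAP average is computed after database lock.

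**Conclusion.** The point holds as a minor one. SAP 19.8 applies a single fixed-divisor formula to a count, where it is correct, and to a rating, where it gives half the recorded score if one day is unscored and that day is skipped or counted as 0. For a child stable at 6 that is 3 instead of 6, or -50%. The set-to-missing alternative costs n but is not in itself an error.

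The conclusion assumes that a stool-free or unfilled day carries no form score, as the wording of Protocol 6.1.13 suggests. The number of children affected is unknown. The reach is one descriptive summary of change and percent change with no hypothesis test. Stool form lies outside the protocol's own variable, given in Protocol 8.3 as "Fecal output (by volume or number of bowel movements per day", and the primary PN/IV volume derivation is not touched.

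**What to change.** Give the form score its own sentence in SAP 19.8: average it over the days in the 48-hour period that have a recorded score, and set it to missing if neither day has one. Keep the divisor of 2 for the stool count when both days are recorded, with a confirmed stool-free day counted as 0. State whether the general diary rule in SAP 17.1.1 covers the output diary, so that the two sections agree.

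The cost is SAP wording and a small programming change. No new data are needed, and no form score changes where both days were scored.
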